### **6.1.3. Nab-Sirolimus Hepatotoxicity Stopping Rules**

Subjects with abnormal hepatic laboratory values (i.e., ALP, AST, ALT, total bilirubin TBL) and/or international normalized ratio (INR) and/or signs/symptoms of hepatitis may meet the criteria for withholding or permanent discontinuation of nab-Sirolimus as specified in the Guidance for Industry Drug-Induced Liver Injury: Premarketing Clinical Evaluation, July 2009.

#### **6.1.3.1. Criteria for Permanent Discontinuation of nab-Sirolimus Due to Potential Hepatotoxicity**

Nab-Sirolimus should be discontinued permanently and the subject should be followed for possible drug-induced liver injury (DILI), if **ALL** of the criteria below are met:

- Total bilirubin  $>2 \times$  ULN or INR  $>1.5 \times$  ULN
- AND increased AST or ALT from the relevant baseline  $\geq 3 \times$  ULN
- AND no other cause for the combination of the above laboratory abnormalities is immediately apparent; important alternative causes for elevated AST/ALT and/or total bilirubin values include, but are not limited to:
  - Hepatobiliary tract disease
  - Viral hepatitis (e.g., Hepatitis A/B/C/D/E, Epstein-Barr Virus, Cytomegalovirus, Herpes Simplex Virus, Varicella, Toxoplasmosis, and Parvovirus)
  - Right sided heart failure, hypotension or any cause of hypoxia to the liver causing ischemia.
  - Exposure to hepatotoxic agents/drugs or hepatotoxins, including herbal and dietary supplements, plants and mushrooms
  - Heritable disorders causing impaired glucuronidation (e.g., Gilbert's Syndrome, Crigler-Najjar syndrome) and drugs that inhibit bilirubin glucuronidation (e.g., indinavir, atazanavir)
  - Alpha-one antitrypsin deficiency
  - Alcoholic hepatitis
  - Autoimmune hepatitis
  - Wilson's disease and hemochromatosis
  - Nonalcoholic Fatty Liver Disease including Steatohepatitis (NASH)
  - Non-hepatic causes (e.g., rhabdomyolysis, hemolysis)

#### **6.1.3.2. Criteria for Conditional Withholding of nab-Sirolimus Due to Potential Hepatotoxicity**

For subjects who do not meet the criteria for permanent discontinuation of ABI-009 and have no underlying liver disease, and eligibility criteria requiring normal transaminases and TBL at baseline or subjects with underlying liver disease and baseline abnormal transaminases, the following rules are recommended for withholding of nab-Sirolimus:

- Elevation of either AST or ALT according to the following schedule:

AST or ALT elevation
>8 x ULN at any time
>5 x ULN but <8 x ULN for ≥2 weeks
>5 x ULN but <8 x ULN and unable to adhere to enhanced monitoring schedule
≥3 x ULN with clinical signs or symptoms that are consistent with hepatitis (such as right upper quadrant pain/tenderness, fever, nausea, vomiting, jaundice).

- OR: Total bilirubin >3 x ULN at any time
- OR: Alk Phos >8 x ULN at any time

Nab-Sirolimus should be withheld pending investigation into alternative causes of DILI. Re-challenge may be considered if an alternative cause for impaired liver tests (ALT, AST, and ALP) and/or elevated TBL is discovered and the laboratory abnormalities resolve to normal or baseline.

## 6.2. **Pazopanib**

### 6.2.1. **Dose Levels for Pazopanib**

Pazopanib starting dose may be at either 400 or 800 mg daily. Pazopanib decrease should be in 200-mg steps, for pazopanib-related AEs that require dose reductions (Section 6.2.2).

Pazopanib dosing may not be reduced below 200 mg daily. Subjects requiring a dose reduction below 200 mg daily should discontinue pazopanib therapy. Pazopanib dosing may not be increased above 800 mg daily. Dose modification algorithms for specific toxicities are detailed below in Section 6.2.2. For all other Grade 3 or 4 non-hematologic toxicities (except alopecia, nausea, or vomiting) that are at least in part attributable to the study drug, the dose should be held until the toxicity resolves to ≤ Grade 1. Treatment should then be resumed at a reduction of one dose level. For recurrent grade 3 or 4 toxicity, the study drug should again be held until the toxicity resolves to ≤ Grade 1 and then reintroduced at another dose level reduction. If the toxicity has abated with reduction of the dose and dose re-escalation is considered safe by the investigator, the study drug dose can then be increased step-wise back to the pre-event dose (in 200 mg increments, after monitoring for 14 days at each dose level to ensure that toxicity did not recur or worsen).

Pazopanib is absorbed orally, with median time to achieve peak concentrations of 2 to 4 hours after the dose. If a dose is missed, it should not be taken if it is less than 12 hours until next dose. For pazopanib dose reduction and stopping rules, please refer to Table 10 and Table 11.

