### 6.2.2. **Pazopanib Dose Modification and Stopping Rules**

Pazopanib is dosed continuously. Modifications to pazopanib dosing should follow the table below. Additional dose reductions may be made outside of the defined parameters below, at

investigator discretion. Dose levels may not be re-escalated outside of the defined guidelines. All dose reductions or re-escalations must be made in 200 mg increments, unless otherwise specified.

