		Recurrent / Worsening Thrombosis	If venous thromboembolic events worsen or reoccur after resumption of pazopanib, permanently discontinue pazopanib.
	Arterial Thromboembolic Events	Any Grade	Discontinue pazopanib.
	ECG QTc Interval Prolonged (Bazett's)	Grade 3	Delay pazopanib until $\leq$ grade 1, then resume pazopanib with one dose level reduction.

		Grade 4	Discontinue pazopanib.
Other	CNS or Pulmonary Hemorrhage	Grade 2 or Greater	Permanently discontinue pazopanib.
	Non-CNS, Non-Pulmonary bleeding	Grade 2	Delay pazopanib until $\leq$ grade 1, then resume with one dose level reduction.
		Grade 3 or 4	Permanently discontinue pazopanib.
	Fistula, perforations, bowel obstruction, or wound dehiscence	Any Grade	
For any grade perforation of any organ, GI leak, or any fistula, discontinue pazopanib.
 
For any grade bowel obstruction requiring medical intervention, delay pazopanib until obstruction resolves completely, and then resume pazopanib at the previous dose. For obstruction requiring surgery delay pazopanib until full recovery from surgery, then resume pazopanib at the previous dose.
 
For wound dehiscence requiring medical or surgical intervention discontinue pazopanib.

	Hemolytic Uremic Syndrome / Thrombotic Thrombocytopenic Purpura	Any Grade	For any grade of hemolytic uremic syndrome (thrombotic microangiopathy) or thrombotic thrombocytopenic purpura, discontinue pazopanib.
	Other Non-Hematologic Grade 3 or 4 Toxicity	Grade 3 or 4	For other grade 3 or 4 non-hematologic toxicity not described above, (excluding nausea, vomiting, and diarrhea; unless refractory to anti-emetics and/or antidiarrheals) and considered at least possibly related to treatment, delay pazopanib treatment until toxicity improves to $\leq$ grade 1, then resume treatment with one dose level reduction.

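### Section 6.2.1 requires a pazopanib reduction for controlled Grade 3-4 diarrhea that Table 10 exempts; separately, Table 11's pazopanib hold for anemia ends on platelets alone

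*Combined protocol and SAP*

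**What the plan says.** **Diarrhea.** Section 6.2.1 first notes: "Dose modification algorithms for specific toxicities are detailed below in Section 6.2.2". It then gives a catch-all, starting "For all other Grade 3 or 4 non-hematologic toxicities (except alopecia, nausea, or vomiting", under which pazopanib is held until Grade 1 or better and resumed one level lower. The only exemptions are alopecia, nausea and vomiting. The catch-all row that ends Table 10 (Section 6.2.2) has the same hold and one-level reduction, but its exemption reads "excluding nausea, vomiting, and diarrhea; unless refractory to anti-emetics and/or antidiarrheals". Diarrhea has no row of its own in Table 10 or Table 11.

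**Which text to follow.** Section 6.2.1 ends with "For pazopanib dose reduction and stopping rules, please refer to Table 10 and Table 11". Section 6.2.2 says "Modifications to pazopanib dosing should follow the table below", and leaves room for judgement: "Additional dose reductions may be made outside of the defined parameters below".

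**Steps and floor.** Reductions are in 200 mg steps with a 200 mg minimum: "Subjects requiring a dose reduction below 200 mg daily should discontinue pazopanib therapy". If the toxicity has abated and the investigator considers it safe, "the study drug dose can then be increased step-wise back to the pre-event dose", in 200 mg increments with 14 days of monitoring at each level.

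**Anemia.** One Grade 3-4 row of Table 11 (Section 6.5) covers thrombocytopenia and anemia. For pazopanib, the hold lasts until platelets are Grade 1 or better, followed by a one-level reduction. For nab-Sirolimus, the same cell requires both a platelet count above 100 x 10^9/L and hemoglobin of at least 8 g/dL.

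**The concern.** Two operative rules give different pazopanib instructions for the same event. Section 6.2.1 reduces the dose for Grade 3-4 diarrhea even when antidiarrheals control it; Table 10 requires nothing unless treatment fails. Two treating investigators at the same center could each follow the protocol and leave similar subjects on different doses. At a 400 mg start there is only one step above the floor, so a second event can decide between full-dose pazopanib and none. Section 2.4 lets a subject continue on nab-Sirolimus alone.

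In phase 1 the ambiguity can pass unseen. Section 6.4 allows Grade 3 diarrhea lasting under 72 hours with adequate supportive care to be excluded as a DLT, so such a subject could count as DLT-free on either 400 or 200 mg.

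The anemia rule has a different fault. Its restart condition does not measure the event that triggered the hold. When hemoglobin falls and platelets do not, the hold has no length, yet the dose is still cut by one level.

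**Working it through.** The plan states no figure to reproduce. The check is a side-by-side reading plus the dose steps.

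**1. The two catch-alls for Grade 3-4 non-hematologic events**

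| Event | Section 6.2.1 | Table 10, last row | In conflict? |
|---|---|---|---|
| Diarrhea, controlled | Hold, reduce one level | Exempt | Yes |
| Diarrhea, refractory | Hold, reduce one level | Hold, reduce one level | No |
| Nausea or vomiting, controlled | Exempt | Exempt | No |
| Nausea or vomiting, refractory | Exempt | Hold, reduce one level | Not in practice: applying Table 10 breaches nothing in 6.2.1 |
| Alopecia | Exempt | Not listed | Lists should match |

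Controlled diarrhea is the live inconsistency.

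**2. Dose consequence of controlled Grade 3-4 diarrhea**

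Inputs: 200 mg step and 200 mg floor (Section 6.2.1); 400 mg start in every Day 1 only cohort (Tables 2 and 8); 800 mg start only in closed cohorts (Tables 1 and 7). Table 10 entries mean no mandated change.

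| Start and event | Section 6.2.1 | Table 10 |
|---|---|---|
| 400 mg, first event | 400 - 200 = 200 mg | 400 mg |
| 400 mg, second event, no re-escalation between | 200 - 200 = 0, below the floor: stop | 400 mg |
| 400 mg, second event after return to 400 mg | 400 - 200 = 200 mg | 400 mg |
| 800 mg, first event | 800 - 200 = 600 mg | 800 mg |
| 800 mg, second event, no re-escalation between | 600 - 200 = 400 mg | 800 mg |

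First-event gap: 200/400 = 50% at the current start; 200/800 = 25% in the closed cohorts.

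**3. Isolated Grade 3-4 anemia, platelets already Grade 1 or better**

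- Table 11 calls for a pazopanib hold.
- The release condition, on platelets, is satisfied at onset, so the delay is zero.
- The reduction still applies as written: 400 - 200 = 200 mg.
- Section 6.2.1 cannot fill the gap, because its catch-all is limited to non-hematologic events.
- No section gives a hemoglobin threshold for pazopanib.
- The 8 g/dL in the nab-Sirolimus part of the cell does not match Section 6.1.2, which requires hemoglobin of at least 9.0 g/dL before nab-Sirolimus on each dosing day.

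**4. How often this could arise**

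Section 1.3 gives any-grade diarrhea of 58% on pazopanib and 16% on placebo in the registrational trial, but no Grade 3-4 rate. Table 3 lists 8 + 3 + 2 + 1 + 1 + 1 + 1 = 17 DLT occurrences, none of them diarrhea or anemia. Events excluded as DLTs would not appear there. Frequency is therefore unknown.

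**The case against.** The strongest reply is that the protocol already points to Table 10. Section 6.2.1 speaks of all *other* toxicities only after referring specific ones to Section 6.2.2, and Table 10 does name diarrhea and attach a condition to it. Section 6.2.1 then sends the reader to the tables, and Section 6.2.2 says to follow the table. Two further places share Table 10's logic: Table 9's diarrhea row for nab-Sirolimus applies only when optimal medication has failed, and the DLT exclusion in Section 6.4 turns on adequate supportive care. Section 6.2.1 is the outlier.

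This stands as an account of the likely intent. It does not remove the problem: the Section 6.2.1 rule is worded as an instruction, nothing withdraws it, and no order of precedence is stated. The discretion in Section 6.2.2 permits an extra reduction but does not say whether this one is required.

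A reader might go further and infer that Table 11's row for other adverse reactions adds a third pazopanib rule, because it tells the investigator to withhold treatment and restart at the same dose. The documents do not support that. Only the Grade 3 line omits the drug; the Grade 4 line names nab-Sirolimus, and the Grade 3 wording repeats the nab-Sirolimus rule in Table 9. The likelier reading is nab-Sirolimus only, so this is a missing label, and no pazopanib doses should be derived from it.

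**Conclusion.** The point holds, with modest practical weight. For controlled Grade 3-4 diarrhea, Section 6.2.1 and Table 10 give 200 mg and 400 mg respectively in the current cohorts. Stopping after a second event follows from Section 6.2.1 only if the dose has not been re-escalated in between. The pazopanib rule for isolated anemia is faulty as written, whatever is decided about diarrhea.

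A reader might infer that the dose-finding result or the phase 2 test is compromised. The documents do not show this: event frequency is unknown, Table 3 records no diarrhea or anemia DLT, and no effect on sample size, alpha, power or PFS is demonstrated. Nor does the point depend on variation between sites, since Section 5.1 names one center and says only that others may join.

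The dose figures assume the stated 200 mg step and floor, an event attributed at least partly to pazopanib, and no discretionary reduction.

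**What to change.** All of this is wording for the next amendment; no new procedures are needed.

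1. **Section 6.2.1.** Change the exemption to: *except alopecia, and except nausea, vomiting and diarrhea unless refractory to anti-emetics and/or antidiarrheals*. Add alopecia to the exemption in Table 10's last row.
2. **Precedence.** State that Table 10 governs pazopanib for non-hematologic events not named in Table 11.
3. **Table 11, Grade 3-4 thrombocytopenia and anemia.** Either state that pazopanib is neither held nor reduced for isolated anemia, or add a hemoglobin restart criterion and say whether the one-level reduction applies. The clinicians must choose. They should not copy 8 g/dL from the nab-Sirolimus part of the cell without first reconciling it with the 9.0 g/dL dosing-day requirement in Section 6.1.2.
4. **Table 11, other adverse reactions (minor).** Label the Grade 3 line *Nab-Sirolimus*, and add *Pazopanib: see Table 10* to both the Grade 3 and Grade 4 lines.

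The cost is that controlled Grade 3-4 diarrhea would no longer trigger an automatic pazopanib reduction. The investigator could still reduce the dose under Section 6.2.2.

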### 6.2.2. **Pazopanib Dose Modification and Stopping Rules**

Pazopanib is dosed continuously. Modifications to pazopanib dosing should follow the table below. Additional dose reductions may be made outside of the defined parameters below, at

investigator discretion. Dose levels may not be re-escalated outside of the defined guidelines. All dose reductions or re-escalations must be made in 200 mg increments, unless otherwise specified.

**Table 10. Dose Modification Algorithms for Adverse Events Possibly Related to Pazopanib (See also Table 9 and Table 11)**

System/Organ	Adverse Event	CTCAE Grade v5.0	Dose modification Algorithm
Skin/Mucosa	Palmar-plantar Erythrodysesthesia Syndrome	Grade 2	Hold pazopanib until resolved to $\leq$ grade 1, then resume with one dose level reduced. If recurrent, consider further dose reduction or discontinuation.
		Grade 3	Permanently discontinue pazopanib.
Lab Abnormalities	Proteinuria	UPC Ratio $\geq$ 2.0 and $<$ 3.0 or urine protein $\geq$ 2.0 g/24 hours and $<$ 3.0	Hold pazopanib until proteinuria resolves to UPC $<$ 2.0 or urine protein $<$ 2.0 g/24 hours, then resume pazopanib at current dose level.
		For UPC Ratio $\geq$ 3.0 and $<$ 4.0 or urine protein $\geq$ 3.0 g/24 hours and $<$ 4.0	Hold pazopanib until proteinuria resolves to UPC $<$ 2.0 or urine protein $<$ 2.0 g/24 hours. Once resolved, resume pazopanib with one dose level reduced.
		For UPC Ratio $\geq$ 4.0 or Nephrotic Syndrome	Discontinue pazopanib.
	Hyperthyroidism / Hypothyroidism	Grade 3 or Grade 4	Discontinue pazopanib.
	Elevated Creatinine	Grade 2	Delay pazopanib until toxicity resolves to Grade 1 or better, then resume pazopanib with one dose level reduction.
		Grade 3-4	Discontinue pazopanib.

Cardiac Toxicity	Hypertension	Grade 3 (Systolic $\geq$ 160, Diastolic $\geq$ 100)	Hold pazopanib until grade $\leq$ 2, then resume pazopanib at 1 dose level reduction.  HOWEVER, if the subject requires hospitalization for management of symptomatic systolic BP $>$ 180 or diastolic BP $>$ 110, permanently discontinue pazopanib.
		Grade 4	Permanently discontinue pazopanib.
	Venous Thrombosis	Grade 2-3, requiring anticoagulation	Delay pazopanib.  If the planned duration of full dose anticoagulation is $\leq$ 2 weeks, omit pazopanib until anticoagulation is completed, then resume pazopanib at same dose. If the planned duration of full dose anticoagulation is $>$ 2 weeks, pazopanib may be restarted at same dose during anticoagulation if all of the following are met:  - The subject must have an in-range INR (usually between 2 and 3) on a stable dose of warfarin or be on a stable dose of LMWH prior to restarting pazopanib.  - The subject must not have any pathological condition that carries a high risk of bleeding.  - The subject must not have had any hemorrhagic events while on study.
		Grade 4	Permanently discontinue pazopanib.
		Recurrent / Worsening Thrombosis	If venous thromboembolic events worsen or reoccur after resumption of pazopanib, permanently discontinue pazopanib.
	Arterial Thromboembolic Events	Any Grade	Discontinue pazopanib.
	ECG QTc Interval Prolonged (Bazett's)	Grade 3	Delay pazopanib until $\leq$ grade 1, then resume pazopanib with one dose level reduction.

		Grade 4	Discontinue pazopanib.
Other	CNS or Pulmonary Hemorrhage	Grade 2 or Greater	Permanently discontinue pazopanib.
	Non-CNS, Non-Pulmonary bleeding	Grade 2	Delay pazopanib until $\leq$ grade 1, then resume with one dose level reduction.
		Grade 3 or 4	Permanently discontinue pazopanib.
	Fistula, perforations, bowel obstruction, or wound dehiscence	Any Grade	
For any grade perforation of any organ, GI leak, or any fistula, discontinue pazopanib.
 
For any grade bowel obstruction requiring medical intervention, delay pazopanib until obstruction resolves completely, and then resume pazopanib at the previous dose. For obstruction requiring surgery delay pazopanib until full recovery from surgery, then resume pazopanib at the previous dose.
 
For wound dehiscence requiring medical or surgical intervention discontinue pazopanib.

	Hemolytic Uremic Syndrome / Thrombotic Thrombocytopenic Purpura	Any Grade	For any grade of hemolytic uremic syndrome (thrombotic microangiopathy) or thrombotic thrombocytopenic purpura, discontinue pazopanib.
	Other Non-Hematologic Grade 3 or 4 Toxicity	Grade 3 or 4	For other grade 3 or 4 non-hematologic toxicity not described above, (excluding nausea, vomiting, and diarrhea; unless refractory to anti-emetics and/or antidiarrheals) and considered at least possibly related to treatment, delay pazopanib treatment until toxicity improves to $\leq$ grade 1, then resume treatment with one dose level reduction.

### **6.3. Dosing Schedules (D1 vs D1/D8)**

Nab-Sirolimus may be dosed on either Day 1 or Day 1/Day 8 of a 21-day cycle, based on which cohort a subject is assigned to. Subjects initially assigned to Day 1/Day 8 dosing may switch to a Day 1 only dosing schedule at investigator discretion, after completion of at least two full cycles of treatment.

Subjects initially enrolled on a Day 1 only schedule may not switch the dosing schedule. Once a subject has switched a dosing schedule, this change is considered permanent and they may not switch back.

### **6.4. Dose Limiting Toxicity**

Dose-limiting toxicities will be assessed in the first 2 cycles (2, 3-week cycles).

A DLT is defined as any Grade 3 or greater AE, at least possibly related to either or both nab-Sirolimus and pazopanib. Only toxicities with a clearly identified and documented alternative explanation may be deemed non-DLT. Dose-limiting toxicities include any death not clearly due to underlying disease or extraneous causes, or persistent intolerable nonhematologic AE of any grade that requires dose reduction or permanent discontinuation of the study-drug, in the opinion of the investigator.

The following adverse events may be excluded from being considered a DLT:

- Grade 3 nausea/vomiting or diarrhea for less than 72 hours, with adequate antiemetic and other supportive care;
- Grade 3 fatigue for less than 1 week;
- Grade 3 or higher electrolyte abnormality that lasts up to 72 hours, is not clinically complicated, and resolves spontaneously or responds to conventional medical interventions.
- Lab abnormalities that have no clinical sequelae (e.g. febrile neutropenia from low ANC, bleeding from thrombocytopenia, etc.) and resolve to grade 1 or better within 7 days will not be considered a DLT.

Nab-Sirolimus dose modification guidelines are outlined in Table 9 and Table 11 for clinically significant toxicities that are deemed related to nab-Sirolimus.

## 6.5. Dose Modification Algorithms for Adverse Events Possibly Related to nab-Sirolimus and Pazopanib

**Table 11 - Dose Modification Algorithms for Overlapping Adverse Events Possibly Related to nab-Sirolimus and Pazopanib (See also Table 9 and Table 10)**

System/Organ	Adverse Event	CTCAE Grade v5.0	Dose Modification Algorithm
Hematologic toxicity	Thrombocytopenia, Anemia	Grade 2	
Nab-Sirolimus: Nab-Sirolimus can be administered if meeting the following hematological requirements: platelets <math>>100 \times 10^9/L</math> and hemoglobin <math>\geq 8</math> g/dL.
 
Pazopanib: No changes to pazopanib dosing.

		Grade 3-4	
nab-Sirolimus: Hold nab-Sirolimus immediately for the remainder of that cycle. Repeat blood collection within 3 days. Nab-Sirolimus can resume once meeting following requirements: platelet count <math>>100 \times 10^9/L</math> and hemoglobin <math>\geq 8</math> g/dL. For 2nd and subsequent events, drug will be restarted at a reduced dose; G-CSF may be given as deemed indicated.
 
Pazopanib: Delay pazopanib until platelets <math>\leq</math> grade 1, resume pazopanib with one dose level reduction.

	Neutropenia, Febrile or Afebrile	Grade 3	
nab-Sirolimus: Hold nab-Sirolimus. Repeat blood collection within 3 days. Nab-Sirolimus can resume once meeting following requirements: absolute ANC <math>\geq 1.5 \times 10^9/L</math>. For 2nd and subsequent events, drug will be restarted at a reduced dose; G-CSF may be given as deemed indicated.
 
Pazopanib: Delay pazopanib until <math>\leq</math> grade 2, and then resume pazopanib at the current dose level.

		Grade 4	
Nab-Sirolimus: Hold nab-Sirolimus. Repeat blood collection within 3 days. Nab-Sirolimus can resume once meeting following requirements: absolute ANC <math>\geq 1.5 \times 10^9/L</math>. For 2nd and subsequent events, drug will be restarted at a reduced dose; G-CSF may be given as deemed indicated.
 
Pazopanib: Delay pazopanib until <math>\leq</math> grade 2, then resume pazopanib with one dose level reduction.

Hepatic Toxicity	Hepatic Failure	Grade 3	
Nab-Sirolimus: See Section 6.1.3.1 and 6.1.3.2.
 
Subjects with ALT/AST > 3 x ULN, or Total Bilirubin > 3 x ULN, or Alk Phos > 8 x ULN are recommended for withholding of nab-Sirolimus.
 
Pazopanib: Discontinue pazopanib.

	ALT, AST, or Bilirubin Elevation	Grade 2	
Nab-Sirolimus: See Section 6.1.3.1 and 6.1.3.2.
 
Subjects with ALT/AST > 3 x ULN, or Total Bilirubin > 3 x ULN, or Alk Phos > 8 x ULN are recommended for withholding of nab-Sirolimus.
 
Pazopanib: Continue pazopanib, but monitor weekly until ALT, AST, and bilirubin return to ≤ grade 1.

		Grade 3-4	
Nab-Sirolimus: See Section 6.1.3.1 and 6.1.3.2.
 
Subjects with ALT/AST > 3 x ULN, or Total Bilirubin > 3 x ULN, or Alk Phos > 8 x ULN are recommended for withholding of nab-Sirolimus.
 
Pazopanib: Delay pazopanib until improved to ≤ grade 1. Restart treatment with one dose level reduction of pazopanib.

	ALT/AST and Bilirubin (Grade 2 or greater ALT/AST elevation with concurrent Grade 2 or greater bilirubin elevation)	Grade 2+	
Nab-Sirolimus: Discontinue nab-Sirolimus.
 
Pazopanib: Discontinue pazopanib.

Other Adverse Reactions	Other Adverse Reactions	Grade 3	Withhold treatment until Grade ≤ 1, then restart at the same dose level. If recurs, restart at 1 dose level lower.

		Grade 4	Permanently discontinue nab-Sirolimus.
--	--	---------	----------------------------------------

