### **6.1.2. Nab-Sirolimus Dose Modification and Stopping Rules**

If treatment cannot be administered on the planned visit date, nab-Sirolimus may be administered  $\pm 3$  days from the scheduled date. Prior to nab-Sirolimus administration, subjects must meet the following hematological requirements for dosing on every dosing day:

- ANC  $\geq 1.5 \times 10^9/L$
- Platelet count  $\geq 100 \times 10^9/L$
- Hemoglobin  $\geq 9.0 \text{ g/dL}$

The treatment may be held (delayed) up to 21 days due to toxicity. Treatment may also be interrupted for situations other than treatment-related AEs such as medical/surgical events or logistical reasons not related to study therapy. Participants should be placed back on study therapy within 21 days of the scheduled interruption, unless otherwise discussed with the Sponsor-Investigator. The reason for interruption should be documented in the subject's study record.

If the dose held or missed was to be Day 1 of the next cycle, the next cycle will not be considered to start until the day the first dose is actually administered to the subject.

If the subject is dosing on a q2/3w schedule, if the dose held or missed was to be Day 8, that week becomes the week of rest. Next dose becomes Day 1 of a new cycle. The cycle with the missed Day 8 dose would become 14 days long versus the normal 21-day cycle. If the cycle with the missed Day 8 dose is Cycle 1 or Cycle 2, the Day 15 visit would also be omitted. If the subject is dosing on a q1/3w schedule, a cycle is not considered to have begun until the subject receives the Day 1 dose. If the subject misses a Day 8 or Day 15 visit, the cycle continues without interruption and the visits are recorded as missed. The following cycle is considered to have begun when the subject receives their next dose.

In the event of clinically significant AE in any part of the study, treatment may be held, and supportive therapy administered as clinically indicated. If the toxicity or event is not grade 3/4 and resolves to baseline or grade 1 in less than or equal to 21 days of stopping therapy, then treatment may be restarted.

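### Table 11 lets nab-sirolimus be given or resumed at hemoglobin ≥8 g/dL, although Section 6.1.2 requires ≥9.0 g/dL on every dosing day; the ALT/AST withholding thresholds also differ

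*Combined protocol and SAP*

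**What the plan says.** Section 6.1.2 sets the general condition for giving nab-sirolimus: "subjects must meet the following hematological requirements for dosing on every dosing day". The list that follows is ANC ≥1.5 x10^9/L, platelets ≥100 x10^9/L and hemoglobin ≥9.0 g/dL, with no exception stated.

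Table 11 in Section 6.5 covers overlapping events possibly related to the two drugs. One of its rows is for thrombocytopenia and anaemia together. For grade 2, "Nab-Sirolimus can be administered if meeting the following hematological requirements", and the requirements are platelets >100 x10^9/L and hemoglobin ≥8 g/dL. For grade 3-4 the drug is held, and then "Nab-Sirolimus can resume once meeting following requirements: platelet count" >100 x10^9/L together with hemoglobin ≥8 g/dL.

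For the liver, Section 6.1.3.2 states that "the following rules are recommended for withholding of nab-Sirolimus". For AST or ALT these are:

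- >8x ULN at any time;
- >5x to <8x ULN, if this lasts at least 2 weeks or the subject is "unable to adhere to enhanced monitoring schedule";
- ≥3x ULN "with clinical signs or symptoms that are consistent with hepatitis".

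Three hepatic cells of Table 11 refer the reader to Sections 6.1.3.1 and 6.1.3.2. They then add that subjects with ALT/AST >3x ULN, total bilirubin >3x ULN or Alk Phos >8x ULN "are recommended for withholding of nab-Sirolimus".

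**The concern.** A site that looks up one laboratory value in two parts of the same protocol can reach opposite dosing decisions. At 8.5 g/dL, Section 6.1.2 bars the dose and Table 11 allows it.

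The band is easy to reach. Entry is allowed at hemoglobin 9 g/dL (Section 3.2), so a small fall on treatment is enough. Myelosuppression was common in the first 13 subjects: 10 of 13 (77%) had it in the first cycle (Section 1.5), and platelet decrease was the leading DLT, with 8 occurrences (Table 3). Those subjects were treated on the earlier Day 1 and Day 8 schedule with pazopanib started at 800 mg, so the rate may differ now.

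The dosing decision has consequences. A held Day 1 dose postpones the start of the next cycle, and the DLT window is counted in cycles (Sections 6.1.2 and 6.4). A delay beyond 21 days needs Sponsor-Investigator approval; otherwise the subject should be discontinued (Section 6.1.2). Stopping nab-sirolimus takes the subject off the study (Section 2.4). In the other direction, dosing at 8.5 g/dL under Table 11 departs from a mandatory safety requirement.

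**Working it through.** This is a comparison of texts. The plan has no figure to reproduce here.

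**Hemoglobin**

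- Section 6.1.2: no dose if hemoglobin is <9.0 g/dL.
- Table 11, grade 2 and grade 3-4 cells: dose or resume if hemoglobin is ≥8 g/dL, given platelets >100 x10^9/L.
- Both conditions hold from 8.0 to <9.0 g/dL. Width: 9.0 − 8.0 = 1.0 g/dL, in 2 cells.

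**Who is affected.** The row covers thrombocytopenia as well as anaemia, and each cell sets a platelet and a hemoglobin condition together. A subject who enters the row through possibly related thrombocytopenia, and whose hemoglobin is 8.5 g/dL for another reason, meets the same ≥8 g/dL condition. A subject with unrelated anaemia and no related thrombocytopenia falls under Section 6.1.2 alone, where there is no conflict.

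**Platelets.** Section 6.1.2 has ≥100 and Table 11 has >100 x10^9/L. They differ only at exactly 100, which is trivial but sits in the same two cells. The neutropenia row of Table 11 uses ANC ≥1.5 x10^9/L, as Section 6.1.2 does. Hemoglobin is therefore the only blood count that differs in substance.

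**ALT/AST, possibly related, without signs or symptoms of hepatitis**

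| Level | Section 6.1.3.2 | Table 11 |
|---|---|---|
| >3x to 5x ULN, any duration | no recommendation to withhold | withholding recommended |
| >5x to <8x ULN, under 2 weeks, enhanced monitoring kept | no recommendation to withhold | withholding recommended |
| >5x to <8x ULN, 2 weeks or more, or enhanced monitoring not kept | withholding recommended | withholding recommended |
| >8x ULN | withholding recommended | withholding recommended |

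The first two lines are the mismatch. Above 3x ULN with signs or symptoms of hepatitis, the two texts agree. The bilirubin (>3x ULN) and Alk Phos (>8x ULN) limits are the same in both places. The sentence stands in 3 cells but matters mainly in 2 (ALT, AST or bilirubin elevation, grade 2 and grade 3-4), because an asymptomatic case in the Hepatic Failure cell is unlikely.

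**Direction.** Table 11 is looser than Section 6.1 on hemoglobin and stricter on ALT/AST. A site cannot be told simply to follow Table 11, or simply to follow Section 6.1, as the more cautious text.

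**The case against.** The best defence is that the protocol already tells sites where to look. Section 6.4 says "Nab-Sirolimus dose modification guidelines are outlined in Table 9 and Table 11 for clinically significant toxicities that are deemed related to nab-Sirolimus". On that view Table 11 is the specific rule for related events and displaces the general one. But the sentence points to guidelines. It does not release anyone from a requirement that applies on every dosing day, and Table 9, which sits inside Section 6.1.2, cross-refers to Table 11 without ranking the two.

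A second defence is that there is a safe reading: Section 6.1.2 says *must* and Table 11 says *can*, so a mandatory condition holds unless it is expressly waived. This stands. It limits the harm, and it is the reason to align Table 11 to 9.0 g/dL. A reader might infer that the deviation status of a dose at 8.5 g/dL cannot be settled at all. That goes too far, since the ordinary reading makes it a departure from Section 6.1.2. What remains is that a site following Table 11 in good faith would make that departure.

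On ALT/AST the defence is stronger. Both texts only recommend, Section 6.1.2 allows treatment to be held for any clinically significant event, and withholding above 3x ULN breaches neither text. The hepatic cells also point back to Section 6.1.3, so they are not silent on the relation between the texts, although a different threshold follows the pointer. A stricter limit for overlapping toxicity of two drugs is plausible. Section 6.1.3.2 refers in part to eligibility criteria with normal transaminases, while this trial admits up to 2.5x ULN (Section 3.2), so its schedule may not have been tailored to this trial. A reader might infer two conflicting mandatory liver rules; the documents do not support that.

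A reader might also infer that the recording of dose delays becomes ambiguous. It does not: the Section 9.2 summaries count what was actually done. Only the dosing decision can vary.

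**Conclusion.** The hemoglobin conflict is real and should be corrected. Two stated safety rules give opposite decisions from 8.0 to <9.0 g/dL for any subject managed under the Thrombocytopenia, Anemia row of Table 11. It would be too narrow to confine this to anaemia judged possibly related. The conclusion rests on reading Table 11 as limited to possibly related events, as its title says, and on finding no waiver of Section 6.1.2 anywhere in the protocol.

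The ALT/AST difference is secondary: a mismatch between two recommendations, confined to the two asymptomatic bands shown above.

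The practical risk is limited. A site that follows the stricter text each time breaches neither, transfusion is allowed (Section 8.1), and one centre is named so far (Section 5.1). The documents do not say how many subjects have fallen in these bands. Table 3 lists no anaemia DLT and one ALT DLT, but it would not show lower-grade events, so it neither proves nor excludes affected subjects. Nothing here bears on alpha, power or sample size.

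**What to change.** In both Thrombocytopenia, Anemia cells of Table 11, set hemoglobin at ≥9.0 g/dL and platelets at ≥100 x10^9/L, to match Section 6.1.2. If 8 g/dL is an intended on-treatment exception, write it into Section 6.1.2 and say to whom it applies.

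For ALT/AST, state one threshold in both Section 6.1.3.2 and the three Table 11 cells. Keep >3x ULN for the combination unless the sponsor confirms that the conditional schedule of Section 6.1.3.2 is what it intends. Importing that schedule into Table 11 by default would loosen a liver-safety limit.

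The cost is a wording amendment, with no new visits, tests or subjects. Holding to 9.0 g/dL may add some dose delays.
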